All study procedures will be conducted virtually by study staff over Partners-approved channels of communication. We expect to consent and evaluate for eligibility up to 160 inpatients at the Gavin CSS in order to achieve our projected randomized sample size of 88 patients with OUD to have 68 participants complete the 10-day trial. Participants will be randomized in a 1:1 ratio to pramipexole 0.25–0.5 mg or equivalent placebo for 10 days.

Eligible patients will be randomized to 10 days of pramipexole or placebo after an initial 3-day screening period to ensure the stability of RLS and opioid withdrawal symptoms. Participants will complete 5 study visits mainly over video or phone: initial screening visit (V1), consent/screening visit (V2), randomization visit (V3), Day 3 interim visit (V4), and an end-of-treatment visit (V5).

Pramipexole will be started at 0.25 mg nightly or identical placebo for the first 3 days. If this dose is well tolerated but not effective after 3 days of treatment, as determined by the day 3 visit, two tablets per night will be given. Note that this means some patients will receive two doses of placebo tablets per night.

All of the participants in this trial are diagnosed with OUD, a condition that may be associated with increased risk of COVID-19-related complications. Thus, considering the safety and psychological wellbeing of our participants, most interactions between participants and study staff will occur remotely. Some visits may take place in person at the Gavin Foundation if virtual visits are considered to be an excess burden to participants or study staff. Necessary precautions, in accordance with MGH policy, will be in place. For the remote visits, research staff will follow the Partners Healthcare requirements for using the appropriate virtual tools: visits will occur via video (Microsoft Teams or other Partners-approved programs) or telephone. A study physician will remain on call in case there any emergent medical or psychiatric issues.

The Gavin Foundation CSS will be provided with a computer that will be used for questionnaires and study visits. This computer will meet all MGB security standards. The Gavin Foundation staff

has agreed to place this computer in a location where participants can complete questionnaires and meet with MGH study staff privately.

V. OVERVIEW OF STUDY PROCEDURES

PRE-SCREEN (VISIT 1):

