This research has potential benefits to society: this study may help other people with OUD and RLS symptoms by adding to the knowledge about this drug, and whether it is a beneficial treatment.

IX. BIOSTATISTICAL ANALYSIS

Analysis of all study data will be conducted by [name], [name], and [name] or another statistician at Partners Healthcare hospitals. All study personnel and participants will remain blinded to treatment assignment, including staff entering study data. Only the hospital Research Pharmacist who generates the randomization code and [name] who will conduct the interim analysis will be unblinded to treatment assignment. The final database will not be unblinded to study staff until all study data are complete and a medical and scientific review by [name] is conducted.

Overview of analytic plan:

We will conduct an interim analysis to probe the futility of the study. We will use the data obtained to date to estimate the effect of randomized treatment group on two outcomes (primary outcome: IRLS score; secondary outcome: SOWS). We will then use this estimate to determine the sample size necessary to detect this effect. To protect the blind, a statistician ([name]) who is not involved in the day-to-day running of the study, will conduct the analyses.

We will perform both intent-to-treat (ITT) analyses (including all patients who received one dose of study medication and complete one assessment post-randomization) and per protocol analyses (including participants with 10 days of evaluable data). Distributions of the outcomes will be examined and data transformation will be applied to satisfy the normality assumptions.

We will analyze data in several ways: comparison of change from randomization to end of Day 5; comparison of change from randomization to end of Day 10; and using all daily values (i.e., longitudinal analyses). The two groups are drug and placebo.

Study endpoints:

The primary outcome (IRLS score) and all secondary and exploratory measures are continuous variables. We will modify the IRLS in two ways: (i) only the symptoms subscale will be employed (only items 1, 2, 4, 6, and 8 will be included); and (ii) the questions will be modified to include symptoms for only the last 24 hours rather than for the previous 7 days. Primary

analyses will focus on the difference in the change in IRLS subscale from randomization to Day 5 and from randomization to Day 10 between the two groups.

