The key secondary variables are the difference from randomization to Day 5 and from randomization to Day 10 in SOWS.

Exploratory analyses will similarly focus on the differences from randomization to Day 5 and from randomization to Day 10. These endpoints include:

- 1. Subjective total sleep time
- 2. Subjective sleep latency
- 3. Subjective time awake after sleep onset
- 4. Depressive (PHQ-9) and anxiety (GAD-7) symptoms
- 5. Time spent in the Gavin CSS

STATISTICAL METHODS

Interim analysis:

(i) Two-sample t-tests will be applied to estimate the effect of randomized treatment group on IRLS subscale score, for the subjects with post-randomization data to date. Using the estimated treatment effect, we will conduct a power analysis to determine the sample size necessary to detect this effect. (i) Two-sample t-tests will be applied to estimate the effect of randomized treatment group on SOWS, for the subjects with post-randomization data to date. Using the estimated treatment effect, we will conduct a power analysis to determine the sample size necessary to detect this effect.

Primary analysis:

(i) Two-sample t-tests will be applied to compare the change in IRLS subscale from randomization to Day 5 and from randomization to Day 10 between the two groups. (ii) Linear mixed-effects models will also be applied to the longitudinally measured IRLS subscale with entry of covariates that correlate with changes in primary endpoints as required (e.g., age, sex, and at-randomization levels of IRLS severity, and SOWS). Subjective sleep measures from the sleep diary for every night of data collection will also be added as potential covariates to the linear mixed-effects models.

Secondary Analysis:

(i) Two-sample t-tests will be applied to compare the change in SOWS from baseline to Day 5 and to Day 10 between the two groups. (ii) Linear mixed-effects models will also be applied to longitudinally measured SOWS with entry of covariates that correlate with changes in primary endpoints as required (e.g., age, sex, and at-randomization levels of IRLS severity, and SOWS).

Subjective sleep measures on every night of data collection will also be added as potential covariates to the linear mixed-effects models.

Exploratory Analyses:

Linear and generalized linear mixed-effects models will be applied to compare changes in the self-reported sleep metrics (e.g., quality, disturbance, sleep latency and duration) across the nights of study and between the groups.

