Linear and generalized linear mixed-effects models and survival-based analyses will be applied to compare the number of days patients continue in CSS treatment between the two groups.

Power/Sample Size:

Power calculations are based on Specific Aims 1 and 2 detailed below. There are insufficient published or unpublished data to perform them on exploratory analyses (detailed above). Meta-analyses of RLS clinical trials indicate that placebo effects using the IRLS are strongly related to the duration of these trials (Fulda et al., 2008). Therefore, we are basing our calculations on short-term trials, similar to our study design, for pramipexole in RLS using abbreviated RLS symptom scales (e.g., Oertel et al., 2007; Manconi et al., 2007, 2012)

Aim 1: The primary outcome is the change in IRLS scale from baseline to Day 10. Using the Oertel et al. (2007) data as reference, with n=34 for each group, we will have 80% power to detect a 6.3 points difference in the change of IRLS scale (with a common standard deviation of the change of 9.0) with a two-sided two-sample t-test at alpha=0.05 level. A change of 3 is considered a clinically meaningful difference from placebo (Allen et al., 2013).

Aim 2: The primary outcome is the change in SOWS. Using the Dunn et al. (2017) data as reference, with n=34, we will have 80% power to detect a 4 points difference in the change of SOWS (with a common standard deviation of the change of 6.0) with a two-sided two-sample t-test at alpha=0.05 level.

Therefore, our plan is to enroll 160 people in a 1:1 drug:placebo ratio in order to randomize 88 patients with OUD and have 68 participants complete the 10-day trial. With approximately 16 patients per week admitted to the CSS with opioid use disorder, and an RLS prevalence of 50% in this context, we do not anticipate any difficulty enrolling to our target sample size for the trial within a 20-month enrollment period.

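### Minor: with 34 completers per group, the Aim 2 t-test has 77% power for a 4-point SOWS difference, not the stated 80%, which needs 4.14 points

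*Combined protocol and SAP*

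**What the plan says.** Section IX, Power/Sample Size, gives one calculation per aim. Aim 1 (IRLS) specifies 34 in each group and claims "80% power to detect a 6.3 points difference in the change of IRLS scale (with a common standard deviation of the change of 9.0"). Aim 2 (SOWS) gives n=34 without saying whether this is per group or in total, and claims "80% power to detect a 4 points difference in the change of SOWS (with a common standard deviation of the change of 6.0"). Both name a two-sided two-sample t-test at alpha 0.05. Aim 2 names no time point.

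The same section then plans to "randomize 88 patients with OUD and have 68 participants complete the 10-day trial", with 1:1 allocation. Section IV gives the same two totals.

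Under Statistical Methods, Secondary Analysis, t-tests will "compare the change in SOWS from baseline to Day 5 and to Day 10 between the two groups", and linear mixed-effects models will be fitted to the longitudinal SOWS data. The Overview of analytic plan defines the intent-to-treat set as "including all patients who received one dose of study medication and complete one assessment post-randomization".

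**The concern.** Every input needed to check the Aim 2 statement is printed beside it, and those inputs do not return the stated power. The standardised effect is smaller in Aim 2 (4/6.0 = 0.667) than in Aim 1 (6.3/9.0 = 0.70). The number, test and alpha are the same, yet both aims are given 80%.

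SOWS is the key secondary variable, so a reader should be able to reproduce its power and know which comparison it describes. What is at stake is the accuracy of one stated figure, not the conduct of the trial.

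**Working it through.** **Inputs** (all from Power/Sample Size): difference 4 points; SD of change 6.0; two-sided two-sample t-test; alpha 0.05; n = 34. The n is read as per group because Aim 1 says so and 68 completers at 1:1 is 34 per group.

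**Step 1. Check the method on Aim 1.** Standardised effect d = 6.3/9.0 = 0.70. Noncentrality = d × √(n/2) = 0.70 × √17 = 2.886. Degrees of freedom = 2 × 34 − 2 = 66, critical t = 1.997. Power from the noncentral t distribution = 81.2%. The n for 80% power is 33.02, so 34 per group. The stated 80% is met, and the method reproduces the plan's other calculation.

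**Step 2. Same method for Aim 2.** d = 4/6.0 = 0.667. Noncentrality = 0.667 × √17 = 2.749. With 66 degrees of freedom and critical t = 1.997, power = **77.3%**. The stated 80% is not reproduced: 80 − 77.3 = 2.7 percentage points.

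**Step 3. Other ways the 80% might have arisen.**

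| Reading | Power for 4 points, SD 6.0 |
|---|---|
| Named t-test, 34 per group | 77.3% |
| Normal approximation, 34 per group: Φ(2.749 − 1.960) | 78.5% |
| Named t-test, 34 in total (17 per group) | 47.0% |
| One-sided t-test, 34 per group (not the named test) | 85.9% |

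None gives 80%.

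**Step 4. What 80% power requires.**
- Holding 34 per group and SD 6.0: the effect detectable with 80% power is d = 0.6896, and 0.6896 × 6.0 = **4.14 points**. By normal approximation it is 4.08 points. Both print as 4 when rounded to a whole number.
- Holding 34 per group and 4 points: SD no larger than 4/0.6896 = 5.80.
- Holding 4 points and SD 6.0: n = 36.3, so 37 per group (80.8%); 36 per group gives 79.7%.

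**Step 5. Effect of rounding in the restatement.** At 34 per group and SD 6.0, a difference of exactly 4.1 points has 79.3% power, and 4.14 points has 80.05%. Two decimals are therefore the safer way to print it.

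**The case against.** The strongest reply is that the sentence is true to its own rounding. Aim 1 is printed to one decimal and Aim 2 to a whole number. If Aim 2 was meant as the difference detectable with 80% power at a fixed 34 per group, the answer is 4.14, and 4 is that answer rounded. This is probably what happened, and it makes the matter small. It does not make the printed statement correct: a reader who enters 4, 6.0 and 34 into the named test gets 77%.

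It can also be said that the intended reading is clear, since 34 per group follows from Aim 1 and the completer total, and the SOWS time points are given under Secondary Analysis. That is fair. Only the power sentence leaves them out.

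A reader might infer three stronger things, none of which the documents support:

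- *The trial is too small and needs 74 completers.* Aim 1's inputs alone lead to 34 per group. The 37 per group in the working only shows what the 4-point statement would require.
- *77% is the power of the whole SOWS analysis.* It belongs to the t-test in 34 completers per group. The plan also has mixed-effects models with covariates, for which it gives no power inputs. The intent-to-treat set requires only one dose and one later assessment, so a comparison in it could include more than 68 people.
- *The interim decision is distorted.* The interim analysis estimates the effects from the trial's own data, and the Aim 2 power figure does not enter that estimate. The projected sample size it is compared with is unchanged.

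**Conclusion.** The Aim 2 power is wrong as written, by a small amount. For the stated difference, SD, number, test and alpha, power is 77.3%, and rounding 4.14 to 4 is the likely cause.

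The conclusion rests on reading n=34 as per group and on taking the 4 points and SD of 6.0 as given; the cited source data were not available to check them. It is limited to the secondary-outcome t-test in the 68 planned completers. It is a minor correction that leaves the sample size and the interim rule as they are.

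**What to change.** In Power/Sample Size, Aim 2:

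1. Replace n=34 with 34 completers per group.
2. Name the time point of the SOWS change to which the calculation applies.
3. State one of two equivalent results, keeping SD 6.0 and the named test: 80% power for a difference of 4.14 points (4.1 to one decimal), or 77% power for a difference of 4 points.

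The cost is an edit to one sentence. No patients, visits or analyses are added.

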Note: The study has had difficulty enrolling study participants. We originally projected that we would be able to enroll all participants within 24 months. Over the two years since we initiated enrollment, we have enrolled 70 of 160 projected participants, which is 43.7% of our enrollment target. During this period, we have randomized 35 of 68 projected participants, which is 51.5% of our randomization target. Due to this delay, we have added an interim analysis to our study protocol to assess the futility of the study. If the needed sample size is smaller than the originally projected sample size, we will continue the study. If the needed sample size is equal to or larger than the originally projected sample size, we will close the study, as we do not have the resources

to continue the study for another 24 months (i.e., the number of months it would take us to continue to recruit, given our current enrollment rate).

X. MONITORING AND QUALITY ASSURANCE

We will use a Data Safety Monitoring Board (DSMB), meeting every 6 months to review the progress of the study. The Board will comprise two research physicians who are familiar with clinical research, restless legs syndrome, OUD, opioid withdrawal, and pramipexole and its effects, but who are not collaborators or close colleagues of the PI or co-investigators. The Board will also include a biostatistician. The DSMB will review all adverse events and unanticipated problems that arise during the study. Adverse events, including serious adverse events, and unanticipated problems will be managed and reported to the IRB. The data to be monitored for safety include: withdrawal symptoms as assessed by SOWS, drug craving as assessed by craving scales, mood and anxiety scales; clinical staff at Gavin Foundation will also monitor for symptoms of hypomania/mania, impulse control disorders. [name] and/or [name], the PI and Investigator and MDs, will review these data as soon as they are available on each participant and at monthly intervals.

XI. REFERENCES

- Allen, R. P. (2013). Minimal clinically significant change for the International Restless Legs Syndrome Study Group rating scale in clinical trials is a score of 3. Sleep Medicine, 14(11), 1229-1229. doi:10.1016/j.sleep.2013.08.001
- American Psychiatric Association. (2013). Diagnostic and statistical manual of mental disorders (5th ed.). Washington, DC: Author.

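### The interim-analysis note measures randomization progress against the completer target (35 of 68, 51.5%) when the plan's target is 88 (39.8%), and its close/continue benchmark has no number or basis.

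*Combined protocol and SAP*

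**What the plan says.** Section IV (Study Design and projected enrollment) gives "our projected randomized sample size of 88 patients with OUD to have 68 participants complete the 10-day trial", from up to 160 consented. Section IX (Power/Sample Size) repeats the plan: "randomize 88 patients with OUD and have 68 participants complete the 10-day trial". The same section bases power on 34 per group, which is 68 in total.

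The note that closes Section IX reports 70 of 160 enrolled over two years and then "we have randomized 35 of 68 projected participants, which is 51.5% of our randomization target". It adds an interim futility look with this rule: "If the needed sample size is equal to or larger than the originally projected sample size, we will close the study". If the needed size is smaller, the study continues. The reason given is a lack of resources "to continue the study for another 24 months", a period explained as "the number of months it would take us to continue to recruit, given our current enrollment rate".

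Statistical Methods (Interim analysis) says how the needed size is obtained: two-sample t-tests "for the subjects with post-randomization data to date", once for IRLS and once for SOWS, and then "Using the estimated treatment effect, we will conduct a power analysis to determine the sample size necessary to detect this effect". It states no power, alpha or dropout allowance.

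**The concern.** The note uses the completer number as the randomization target, so progress looks further along than the plan's own target implies. The remaining time seems to carry the same slip.

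The larger issue is the rule beside it. The decision to stop the trial depends on a benchmark that has no number. The note applies the word projected to 160 and to 68, and Section IV applies it to 88. Nor does the plan say whether the needed size counts completers or randomized patients, or which of the two outcomes decides. A rule left open in this way could be settled after the interim effect has been seen, which is what pre-specification is meant to prevent.

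**Working it through.** **Inputs.** From Sections IV and IX: 160 enrolled, 88 randomized, 68 completers. From the note: 70 enrolled and 35 randomized in 24 months. From Power/Sample Size: IRLS difference 6.3 with SD 9.0; SOWS difference 4 with SD 6.0; n = 34 per group; two-sided t-test at 0.05.

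**Progress.**
- The plan's figure: 35/68 = 51.5%. The division is right, but 68 = 2 × 34 is the completer number.
- Against the stated randomization target: 35/88 = 39.8%.

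**Remaining time** = (target − achieved) / (achieved / 24).

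| Target | Calculation | Months |
|---|---|---|
| 160 enrolled | 90 / (70/24) | 30.9 |
| 88 randomized | 53 / (35/24) | 36.3 |
| 68 randomized | 33 / (35/24) | 22.6 |

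The stated 24 months is near only the last row, which is not a planned target.

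**Power as planned.** Noncentral t, 2n − 2 degrees of freedom, noncentrality d√(n/2).
- IRLS: d = 6.3/9.0 = 0.70. At 34 per group power is 81.2%, so the plan's 80% reproduces. At 33 per group it is 79.97%, so the t-test needs 34 per group, N = 68. The normal approximation gives 32.04, rounded up to 33 per group, N = 66.
- SOWS: d = 4/6.0 = 0.667. At 34 per group power is 77.3% (78.5% by normal approximation), not 80%. The t-test needs 37 per group, N = 74; the normal approximation gives 35.3, rounded up to 36 per group, N = 72. At 34 per group, 80% power corresponds to d = 0.6896, or 0.6896 × 6.0 = 4.14 points.

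**The rule with an uninflated needed N.** Power of 80% and two-sided 0.05 are assumed to carry over from Power/Sample Size.
- Continue against 68: needed N at most 66, so 33 per group, d ≥ 0.7003.
- Continue against 88: needed N at most 86, so 43 per group, d ≥ 0.6112.
- Between these values, 68 closes the study and 88 continues it. The SOWS design effect (0.667, N = 74) lies inside the band. The IRLS design effect (0.70, N = 68) lies at its upper edge: by the normal approximation, N = 66 continues under both.
- A benchmark of 160 would be looser still. An IRLS difference of 5.0 with SD 9.0 needs N = 104, which closes against 68 and 88 but continues against 160.

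**The rule on a common basis.** Dividing the needed N by the planned retention, 68/88, and comparing it with 88 gives N × 88/68 < 88, which is the same condition as N < 68. For IRLS, 68 becomes 88, equal to 88: close. For SOWS, 74 becomes 95.8, above 88: close. The two benchmarks then always agree.

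**Sensitivity.** At 90% power the design effects need N = 88 (IRLS) and 98 (SOWS), and both close against 68 and against 88.

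**The case against.** The strongest reply is that progress and months are not inputs to the rule, which turns only on the needed size against the projected size. That stands. A reader might infer that the mislabelled target drives the closing decision; the documents do not support this. Lower progress and a longer remaining time would, if anything, strengthen the stated reason for an interim look.

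It can also be said that 68 is the natural benchmark, because the note uses that number and a t-test calculation yields an analysable N, so that a conflict arises only if an uninflated N is set against a dropout-inflated 88. That is largely right, and it is why the conflict is conditional. But the text does not say so, and Section IV's wording points to 88.

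Two stronger readings should be resisted. One is that 36 months is the correct replacement figure. The note refers to the enrollment rate, which for 160 enrolled gives 30.9 months; the documents do not settle which basis was meant. The other is that the trial will stop at 68 randomized and so fall short of 68 completers. No section says this; the plan still randomizes 88.

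Finally, 4.14 SOWS points rounds to the stated 4. That makes the SOWS item minor, but 80% is still not the power of the stated test.

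**Conclusion.** The point holds as an inconsistency in the target together with an underspecified stopping rule. Progress is 39.8%, not 51.5%, and this rests only on the plan's own figures. The 24 months is understated on either planned target, by about 7 months (160 enrolled) or 12 months (88 randomized), assuming the observed rates continue.

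The benchmark ambiguity can reverse the decision, but only if a needed N without dropout allowance is compared directly. At an assumed 80% power and two-sided 0.05, the affected range is d from about 0.61 to 0.70, which contains the SOWS design effect. A reader might infer that 68 and 88 are inherently rival rules. They are not: on a common basis they are the same rule. The gap is that the plan fixes neither the number, the basis, the power settings nor the governing outcome. The primary IRLS power statement is sound.

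**What to change.** - Correct the note to 35 of 88 randomized (39.8%), or report completers to date against 68.
- Restate the remaining time with its basis: about 31 months for 160 enrolled, or about 36 months for 88 randomized, at the observed rates.
- Before the interim, state the benchmark as a number on the same basis as the needed size: needed completers against 68 or, equivalently, needed N divided by 68/88 against 88.
- State the power, alpha, formula and rounding, since the IRLS design effect turns on them (68 by t-test, 66 by normal approximation). Say whether IRLS or SOWS governs, or how the two combine.
- Restate SOWS as about 77% power for 4 points with 34 per group, or 80% for about 4.1 points.

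No patients or data are added. Progress, remaining time and SOWS power will look less favourable. Fixing the benchmark is also a decision of substance: it removes the lenient reading (uninflated N against 88), so by the t-test at 80% power an interim effect equal to either design effect would close the study.

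### The interim go/no-go rule closes the trial about half the time when the drug works exactly as the design assumes, and its key terms are undefined

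*Combined protocol and SAP*

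**What the plan says.** Statistical Methods, Interim analysis, estimates the treatment effect on IRLS and on SOWS by t-test from the data to date, and then: "Using the estimated treatment effect, we will conduct a power analysis to determine the sample size necessary to detect this effect". The Note at the end of Power/Sample Size turns this into a decision. The study continues if the needed number is smaller than the one first projected; otherwise, "If the needed sample size is equal to or larger than the originally projected sample size, we will close the study".

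The purpose is given as futility: "we have added an interim analysis to our study protocol to assess the futility of the study". The reason for closing is different: "we will close the study, as we do not have the resources".

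The projected size appears in three forms. Section IV gives a "projected randomized sample size of 88 patients with OUD to have 68 participants complete the 10-day trial". The Note says "we have randomized 35 of 68 projected participants, which is 51.5% of our randomization target", and also calls 160 enrolled participants projected.

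The power statements are, for Aim 1, "we will have 80% power to detect a 6.3 points difference in the change of IRLS scale" (34 per group, SD 9.0, two-sided alpha 0.05) and, for Aim 2, "we will have 80% power to detect a 4 points difference in the change of SOWS" (SD 6.0, same n). Neither allows for the interim rule.

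**The concern.** A sample size recalculated from the observed effect is smaller than the original only when the observed effect is larger than the one the original was built on. If the true effect equals the design effect, the interim estimate falls above or below it about equally often, so the rule comes close to a coin toss under the very scenario the trial was powered for.

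Two things follow. The 80% in the Aim 1 statement does not describe the trial as it will be run. And a closure would say little about pramipexole while carrying the label of futility.

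The rule also cannot be carried out without further choices: which benchmark, what recalculation power, which of two outcomes decides, and what final size applies if the study continues. The interim time point and the direction of benefit are not specified either. The analyst will be unblinded, so choices left open could be made with treatment results in view.

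**Working it through.** **Inputs.** From Power/Sample Size: effect 6.3, SD 9.0 (d = 0.70), 34 per arm, two-sided alpha 0.05; for SOWS 4/6.0 = 0.667. From the Note: 35 randomized, about 17 per arm. The evaluable number is not given; applying the planned retention, 35 × 68/88 = 27, gives 13 per arm as a lower case. Assumption: the ratio 0.70, stated for the IRLS scale, carries over to the five-item 24-hour subscale.

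**1. The plan's own figure.** Noncentral-t power at d = 0.70 and 34 per arm is 81%, so the Aim 1 statement is right for a fixed design.

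**2. The plan's assumptions fed into the rule.** At 80% power, d = 0.70 needs 33.02 per arm, rounded up to 34, total 68: equal to 68, so close. SOWS at d = 0.667 needs 36.3, rounded up to 37, total 74: larger, so close.

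**3. Threshold for continuing.** The effect at which the needed n falls below 34 per arm is 0.690 SD (n unrounded) or 0.700 SD (n rounded up). With SD 9.0 that is 0.690 × 9.0 = 6.2 or 0.700 × 9.0 = 6.3 points.

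**4. Probability of closing at d = 0.70, 17 per arm.** With known SD, Φ((0.690 − 0.70)/√(2/17)) = Φ(−0.03) = 49%. By exact noncentral t it is 48.2% (threshold 0.690) or 49.4% (0.700).

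**5. Overall power** (continue, then significant at 34 per arm), by simulation of two-stage trials at d = 0.70:

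| Reading | Closed | Power |
|---|---|---|
| No interim rule | – | 81% |
| IRLS, 68, 80%, 17/arm | 48–49% | 49–50% |
| IRLS, 68, 80%, 13/arm | 48–49% | 48–49% |
| IRLS, 88, 80%, 17/arm | 39% | 58% |
| IRLS, 160, 80%, 17/arm | 23% | 70% |
| IRLS, 68, 90%, 17/arm | 60% | 39% |
| Either outcome passes, 68, 80% | 30–35% | 60–63% |
| Both must pass, 68, 80% | 65–70% | 29–34% |

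The two-outcome rows assume a correlation of 0.3–0.6 between outcomes, which the documents do not give. The most lenient combination tried (either outcome, benchmark 160, correlation 0) gives 6% closed and 78% power. If a continuing study runs to the recalculated n instead of 34 per arm, power is 47–49%. If 68 is a randomized total with 68/88 retained (about 53 completers, 26 per arm), power is 70% without the rule and 46–48% with it.

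**6. Which benchmark the Note seems to mean.** Reaching 68 randomized takes 33 more: 33/35 × 24 = 22.6 months, which fits the further 24 months it mentions. Reaching 88 takes 53 more: 53/35 × 24 = 36.3 months.

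**7. What a closure shows.** At 17 per arm and SD 9.0 the 95% CI half-width is 2.037 × 9.0 × √(2/17) = 6.29 points. An observed benefit anywhere from about 0 to 6.2 points closes the study while the interval still contains 6.3. At the threshold itself, t = 0.690 × √(17/2) = 2.01, an interim p of about 0.05, and conditional power at 34 per arm is about 90%. Of the trials closed at the design effect, (81.2 − 49.7)/48.2 = 65% would have been significant at 34 per arm.

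**The case against.** Five points deserve weight.

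- **Rounding.** Step 2 for IRLS is a knife-edge. The normal formula gives 32.04, so 33 per arm and 66 in total, which would continue. This stands, but it moves the closure probability only to about 47% and power to about 51%. The SOWS result partly reflects a separate matter: 34 per arm gives about 77% power for Aim 2.
- **Conditional headline.** The figure of about 50% depends on a reading, and section IV does call 88 the projected randomized number. That is true, and why the alternatives are shown. IRLS and 80% are the ordinary defaults, and the Note's own 68 and 24 months favour that benchmark.
- **Resources.** The sponsor says it cannot recruit for another 24 months, so an uninterrupted trial at 81% may not be on offer. That is a legitimate reason to stop. It does not make the stated 80% correct, nor a closure informative about the drug.
- **Disclosure.** The resource reason is openly given, and nothing says closure will be reported as evidence against pramipexole. Fair; the remedy is to say so explicitly.
- **Pilot status and units.** The trial is titled a pilot, the rule does not inflate type I error, and the point-scale figures need SD 9.0 to hold on the subscale. The conclusions in SD units need only the ratio 0.70.

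**Conclusion.** The concern holds. With IRLS deciding, 80% recalculation power and a benchmark of 68, the rule closes 48–49% of trials in which the design effect is true and lowers power from 81% to 48–50%. With benchmark 88 the figures are 39% and 58%; with 160 they are 23% and 70%. Unless noted, these assume a final 34 per arm and about 17 per arm at the look; 13 per arm changes the main result little. The exact loss cannot be read from the plan because the terms that determine it are missing, but power fell below 80% in every variant examined. Because this is the trial's go/no-go decision, it must be fixed before the interim data are seen.

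**What to change.** 1. Define the rule: the benchmark (68 completers or 88 randomized, comparing like with like), the recalculation power, the direction of benefit and the final size if the study continues. State that IRLS subscale change from randomization to Day 10, the Aim 1 outcome, decides, with Day 5 and SOWS descriptive at the interim.
2. Restate the power for Aim 1 with the rule in force, together with the probability of closing when the design effect is true.
3. Describe closure under this rule as a feasibility closure, not futility. Report the estimate with its 95% CI, and state how many further participants can be funded.

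The cost is wording and one simulation, with no added participants. The price is candour: on the natural reading the stated power drops to about 50%, and a closed trial cannot be presented as a negative result.

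A true futility rule is optional. For example, non-binding conditional power under the design effect with a 20% cut-off at 17 per arm would close 1.6% of trials at d = 0.70 and 46% under the null, keeping power at 81%. It would also send about 98% of trials at the design effect and 54% of null trials on to 34 per arm, which the Note says the sponsor lacks the resources to do.
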